6.4.2.5. Clinical Safety Laboratory Investigations

Not applicable.

Statistical Analysis Plan

| | | |
|--|------------|------------------|
| Study alias & e-track number(s): V59 77 (205352) | Version: 1 | Date: 19-09-2016 |
|--|------------|------------------|

 GSK GlaxoSmithKline

6.4.2.6. Concomitant Medication

The frequencies and percentages of subjects reporting concomitant medications will be tabulated overall and by study group. Medications (generic drug name) will be coded using the WHODRUG dictionary (see section 11.2 for definition).

7. ANALYSIS INTERPRETATION

Except for analysis on primary immunogenicity objective with predefined success criterion, comparative analyses are descriptive with the aim to characterize the difference between groups. The use of these descriptive analyses should be limited to supportive analysis of confirmatory analyses or hypothesis generation. There are no success criteria associated with the secondary immunogenicity objectives in this study.

With respect to confirmatory analyses the interpretation must be done in a hierarchical manner. To demonstrate immune response sufficiency after MenACWY-CRM booster vaccine administration, the lower limit of the one-sided 97.5% Confidence Interval (CI) for percentage of subjects with hSBA booster seroresponse against each of serogroups A, C, W and Y must be greater than 75%. This will be tested sequentially first in the group of subjects who received primary vaccination with Menveo and, if met, also in the group of subjects who received primary vaccination with Menactra.

Null hypothesis: $P_{ij} \leq 0.75$

versus

Alternative hypothesis: $P_{ij} > 0.75$

Where: P_{ij} is the population booster seroresponse rate; $j = 1, 2$ refer to group Menveo-Menveo (first test) and Menactra-Menveo (second test) respectively; $i = 1, 2, 3, 4$ refer to serogroup A, C, W and Y respectively. Overall significance level for all hypothesis tests is one-sided $\alpha = 2.5\%$.

Note that the lower limit of the 1-sided 97.5% CI corresponds to the lower limit of the 2-sided 95% CI that will be presented in the statistical output.

| Statistical Analysis Plan | |  GSK GlaxoSmithKline |
|--|------------------|---|
| Study alias & e-track number(s): V59 77 (205352) | Version: 1 | |
| | Date: 19-09-2016 | |

The study will be considered successful if the immune response sufficiency will be demonstrated at least in the group of subjects who received primary vaccination with Menveo.

8. CONDUCT OF ANALYSES

8.1. Sequence of analyses

| Description | Analysis ID | Disclosure Purpose (CTRS=web posting, SR=study report, internal) | Dry run review needed (Y/N) | Study Headline Summary (SHS)requiring expedited communication to upper management (Yes/No) | Reference for TFL TOC |
|----------------|-------------|--|-----------------------------|--|--|
| Final analysis | E1_01 | SR and CTRS | Y | Yes | All tables from TFL TOC 25-JUL-2016 |

8.2. Statistical considerations for interim analyses

No interim analysis of data from this study is planned.

9. CHANGES FROM PLANNED ANALYSES

None

10. LIST OF FINAL REPORT TABLES, LISTINGS AND FIGURES

The TFL TOC provides the list of tables/listings and figures needed for the study report. It also identifies the tables eligible for each analyses and their role (synopsis, in-text, post-text, SHS...)

| Statistical Analysis Plan | |  GlaxoSmithKline | |
|--|------------------|---|--|
| Study alias & e-track number(s): V59 77 (205352) | | | |
| Version: 1 | Date: 19-09-2016 | | |

The mock tables referred under column named 'layout' can be found in the legacy-NV SDD dedicated folder for standard tables.

The following group names will be used in the TFLs:

| Group order in tables | Group label in tables | Group definition for footnote | Pooled Groups label in tables | Pooled definition for footnote |
|-----------------------|-----------------------|--|---------------------------------|---|
| 1 | Menveo-Menveo | Subjects previously vaccinated with Menveo | Pooled Menveo/Menactra - Menveo | Subjects previously vaccinated with Menveo/Menactra |
| 2 | Menactra-Menveo | Subjects previously vaccinated with Menactra | Pooled Menveo/Menactra - Menveo | Subjects previously vaccinated with Menveo/Menactra |
| 3 | Naive | Naive subjects | Naive | Naive subjects |

11.2. Standard data derivation

Immunogenicity

Values below the limit of quantification (recorded as “< LQ”) will be set to half that limit.

Statistical Analysis Plan

| | | |
|--|------------|------------------|
| Study alias & e-track number(s): V59 77 (205352) | Version: 1 | Date: 19-09-2016 |
|--|------------|------------------|

 GSK GlaxoSmithKline

Seroresponse is defined for this booster study as follows:

- for subjects with pre-vaccination titers <4, post-vaccination titers \geq 16;
- for subjects with pre-vaccination titers \geq 4, post vaccination titers at least 4 times the pre-vaccination titers.

Duration in the Study

Duration in the study is defined in days as:

Last visit date (visit x)^a – Enrollment date (visit 1) + 1

^aor premature discontinuation date (in case of withdrawal from the study)

The duration is missing if one of the dates is missing or incomplete.

Unsolicited Adverse Events

All adverse events will be characterized according to the date of occurrence related to the vaccination phase as follows:

- **Emergence before vaccination phase:** start date before the first date of injection of study vaccine.
- **Emergence during vaccination phase:** start date on or after the first date of injection of study vaccine or, adverse event increase in severity including to “serious” adverse event.

If start date is equal to the first date of injection then “timing” variable (“On injection day, before injection”/“On injection day, after injection”) will be used to define whether the adverse event occur before or after the injection.

If an adverse event start date is missing or unknown, the adverse event will be considered as emergent.

When start and/or end dates of an adverse event are only partially known, adverse events will be categorized as emergent before, during, or after vaccination phase using the following rules:

Statistical Analysis Plan

| | | |
|--|------------|------------------|
| Study alias & e-track number(s): V59 77 (205352) | Version: 1 | Date: 19-09-2016 |
|--|------------|------------------|

 GSK GlaxoSmithKline

- If the partial end date is before ($<$) the first study vaccination (i.e., year or year & month is/are before the first study vaccination year or year & month) then the adverse event is emergent before vaccination phase.
- If the partial start date is equal or after (\geq) the first study vaccination (i.e., year or year & month is/are after or the same as the first study injection year or year & month) then the adverse event is emergent during vaccination phase.

The **maximum event severity** is the greatest severity associated with a preferred term for a reported adverse event according to the following order: Mild < Moderate < Severe. Unknown/ Missing severity is considered as severe (except for the definition of emergence).

Multiple AEs with the same PT for the same subject are counted only once.

Vaccination-related Adverse Events are those for which the cause has been evaluated by the investigator, and recorded either as possibly related, probably related or unknown/missing.

Prestudy, Concomitant and Post-Vaccination Medications

A previous medication is a medication used only before the first study vaccination (i.e. medication end date < first study vaccination date).

A post-vaccination medication is a medication used only after study vaccination + 28 days (i.e. medication start date $>$ last study vaccination date + 28 days).

All other medications are concomitant

When start and/or end dates of a medication intake are missing, the medication is considered as concomitant with the study vaccination schedule.

If the first study vaccination date is missing then the medication is considered as concomitant with the study vaccination schedule, provided that the study vaccine was administered to the subject.

The business rule can be consulting by clicking on the following icon:

| | | | |
|--|------------------|---|--|
| Statistical Analysis Plan | |  GlaxoSmithKline | |
| Study alias & e-track number(s): V59 77 (205352) | | | |
| Version: 1 | Date: 19-09-2016 | | |

 NV business
 rule.docx

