6.5 Prior and Concomitant Medications and Vaccines

All medications, vaccines and blood products taken or received by the subject within 30 days prior to the start of the study are to be recorded on the Prior and Concomitant Medications CRF.

In addition, the following are considered prior medications for this protocol: all medication/vaccines described in the inclusion and exclusion criteria of this protocol including:

- Systemic administration of corticosteroids (PO/IV/IM) for more than 14 consecutive days within 90 days prior to study vaccination;
- Administration of antineoplastic and immunomodulating agents or radiotherapy within 90 days prior to study vaccination;
- Immunglobulins or any blood products within 180 days prior to informed consent;
- Systemic antibiotic treatment within 3 days prior to study vaccination or blood draw;
- Any investigational or non-registered medicinal product within 30 days prior to study vaccination;
- Administration of vaccines within 7 days (for inactivated vaccines) or 14 days (for live vaccines) prior to vaccination in this study or who are planning to receive any vaccine within 28 days from the study vaccination

Use of analgesics/antipyretics to prevent or treat solicited AEs will be captured in the Subject Diary from day 1-7 following each vaccination. Medications taken for prophylaxis are those intended to prevent the onset of symptoms. Medications taken for treatment are intended to reduce or eliminate the presence of symptoms that are present.

Concomitant medications include all prescription and non-prescription medications (including vaccines) taken by/administered to the subject during the 30 days after study vaccination and must be documented on the Concomitant Medications CRF. Mineral supplements and vitamins are not considered concomitant medications.

When recording concomitant medications/vaccine, they should be checked against the study entry and continuation criteria in [Section 4, Selection of Study Population](#) to ensure that the subject should be enrolled/continue in the study.

Concomitant medication administered for treatment of AEs with medically-attended visits, AEs leading to study withdrawal and SAEs must be documented during the entire study period.

Any vaccine not foreseen in the study protocol in the period starting at Day 1 and ending at Day 181 must be recorded in the eCRF.

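### SAP 11.2: the missing-date sentence contradicts the section's own definitions of previous and post-vaccination medication for two date patterns

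*SAP*

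**What the plan says.** The relevant text is the part of SAP 11.2 on prestudy, concomitant and post-vaccination medications. It gives four statements in this order.

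- Previous: "A previous medication is a medication used only before the first study vaccination (i.e. medication end date < first study vaccination date".
- Post-vaccination: "A post-vaccination medication is a medication used only after study vaccination + 28 days", made operational as "medication start date $>$ last study vaccination date + 28 days".
- Residual: "All other medications are concomitant".
- Missing dates: "When start and/or end dates of a medication intake are missing, the medication is considered as concomitant with the study vaccination schedule".

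No order of precedence is stated, there is no exception for a record whose known date already decides the class, and ongoing medications are not mentioned. The section ends with a pointer to an embedded business-rule file, whose content is not part of the documents available here.

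The classification is used in SAP 6.4.2.6: "The frequencies and percentages of subjects reporting concomitant medications will be tabulated overall and by study group".

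Protocol 6.5 has medications recorded on both sides of the window. Everything taken in the 30 days before study start is captured. At the other end, treatment given for medically attended AEs, AEs leading to withdrawal and "SAEs must be documented during the entire study period".

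**The concern.** The definition of *previous* tests the end date and nothing else. The definition of *post-vaccination* tests the start date and nothing else. One known date can therefore settle the class. The missing-date sentence is triggered when either date is absent, so it also captures records that the definitions have already classified, and gives them a different answer.

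Two programmers working from this section could each defend a different table. If the sentence is applied as written, drugs known to have stopped before vaccination, or known to have started after the 28-day window closed, are counted as concomitant. The table then overstates concomitant use as the SAP itself defines it.

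**Working it through.** The plan states no figure to reproduce, so the check compares the two rules pattern by pattern.

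**Inputs, all from SAP 11.2.** Set the vaccination date V = 0. There is a single vaccination, so first and last vaccination coincide. Let s be the start date and e the end date, in days from V.

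**Rule A, the definitions by their own date tests.** Previous if e is known and e < 0; otherwise post-vaccination if s is known and s > 28; otherwise concomitant.

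**Rule B, the missing-date sentence read literally.** Concomitant if s or e is missing; otherwise as Rule A.

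| Start s | End e | Rule A | Rule B | Conflict |
|---|---|---|---|---|
| -40 | -5 | previous | previous | no |
| +90 | +100 | post-vaccination | post-vaccination | no |
| missing | -5 | previous | concomitant | **yes** |
| +90 | missing | post-vaccination | concomitant | **yes** |
| -40 | missing | concomitant | concomitant | no |
| +10 | missing | concomitant | concomitant | no |
| missing | +10 | concomitant | concomitant | no |
| missing | +100 | concomitant | concomitant | no |
| missing | missing | concomitant | concomitant | no |

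Of the nine patterns, seven have a missing date. In five of those seven the residual class already gives concomitant, so the missing-date sentence adds nothing. In the other two it changes the class, and in both the known date was decisive. The sentence therefore has an effect only where it contradicts the definitions.

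**Contrast within SAP 11.2.** For adverse events the section says: "When start and/or end dates of an adverse event are only partially known, adverse events will be categorized as emergent before, during, or after vaccination". Under those rules, a partial end date that lies before vaccination is enough to place the event before vaccination. The medication sentence sets aside even a complete end date before vaccination.

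**Can the records occur?** Protocol 6.5 collects pre-study medications, and AE treatments to the end of follow-up at Day 181, so both conflicting patterns are possible. The documents do not say how often.

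**The case against.** **The sentence may be meant as a fallback.** It follows the definitions and could be read as covering only records that they leave unsettled. But those records already fall into the residual class, so on that reading the sentence does nothing. The text also does not say so, and its and/or wording points the other way.

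**The business-rule file may set precedence.** It may, and it cannot be checked here. How the records will actually be programmed is therefore not established. The SAP sentence still conflicts with the definitions beside it and would have to agree with that file.

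**Defaulting to concomitant is cautious.** The AE rules likewise treat an event with a missing start date as emergent. This stands where the dates are uninformative, and nothing there needs to change. It does not justify overriding a date that rules out use in the window.

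**The protocol uses the term more widely.** Protocol 6.5 also calls late AE treatment concomitant medication. That is correct, but the SAP gives its own date-based classes, and the conflict lies inside them.

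**Ongoing drugs.** A reader might infer that every drug begun late and still being taken at Day 181 is misclassified. The documents do not support that. Elsewhere the SAP refers to ongoing adverse events as a state in its own right, and it does not say that an ongoing medication has a missing end date. If ongoing is a recorded status, only a truly unknown end date triggers the second pattern. The first pattern needs no such assumption.

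**Size.** A reader might also try to quantify the over-count. If 10% to 30% of the 630 planned evaluable subjects started a recorded treatment after Day 29, and 10% to 25% of those were ongoing, then 630 × 0.10 × 0.10 = 6.3 and 630 × 0.30 × 0.25 = 47.25, or 1.0% to 7.5% of 630. None of these rates is in the documents. The result also depends on ongoing being stored as missing. It counts subjects with such a record, not the error in the table, because a subject with any other concomitant drug is already in the overall count. It should not be used.

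**Group comparison.** Bias between the study groups might be inferred as well. Nothing in the documents bears on whether date completeness differs by group, and SAP 6.4.1 rules out statistical comparison of safety parameters between groups.

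**Conclusion.** The contradiction is real and narrow. Two missing-date patterns receive one class from the definitions and another from the missing-date sentence: unknown start with an end before vaccination, and start more than 28 days after vaccination with a missing end. The second extends to ongoing drugs only under an assumption about data storage that the SAP leaves open.

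Applied literally, the sentence inflates the concomitant-medication table of SAP 6.4.2.6. The direction is clear, but the amount cannot be estimated from the documents. Nothing else is affected. Exclusion from the per-protocol set for forbidden medication runs through deviation code 230 (SAP 5.2.3.1 and Annex 2), which is not linked to this derivation. The primary seroresponse analysis and the power calculation do not use it. This is a minor correction to a descriptive output, subject to the caveat that the embedded business-rule file could not be seen.

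**What to change.** Replace the missing-date sentence in SAP 11.2 with:

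> A medication with a known end date before vaccination is previous, and one with a known start date more than 28 days after vaccination is post-vaccination, even if the other date is missing or the medication is ongoing; it is treated as concomitant only when the available date(s) cannot rule out use between vaccination and vaccination + 28 days.

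Align the embedded business-rule file with this wording. In the table above, only the two conflicting rows change. The other five missing-date patterns stay concomitant, so the cautious default is kept where it is needed, and the handling of ongoing drugs becomes explicit.

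The cost is one SAP sentence and a small change to the derivation program. No new data are required.

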12. ANNEX 2: SUMMARY ON ELIMINATION CODES

Table 12-1 Safety Sets

| PD code | PD Description | Study Period | All Exposed Set | Safety Set, Unsolicited AEs | Safety Set, Solicited AEs |
|---------|--|--------------|-----------------|-----------------------------|---------------------------|
| | Exclusion code | | EXPFL | SSUFL | SSSFL |
| 100 | Study vaccine not administered AT ALL | D1-D181 | EXC | EXC | EXC |
| 115 | Subject did not provide any post-vaccination unsolicited safety data | D1-D181 | None | EXC | None |
| 116 | Subject did not provide any post-vaccination solicited safety data | D1 | None | None | EXC |

EXC = excluded from this analysis set.

Statistical Analysis Plan

Study alias & e-track number(s): V59 77 (205352)
 Version: 1

Date: 19-09-2016

Table 12-2 Immunogenicity Sets

| PD code | PD Description | Study Period | FAS Day 1 | FAS Day 29 | PPS Day 1 | PPS Day 29 |
|---------|---|--------------|------------------|------------------------------------|------------------|---|
| | | | FAS01FL | FAS29FL | PPS01FL | PPS29FL |
| 100 | Study vaccine not administered AT ALL | D1-D181 | EXC | EXC | EXC | EXC |
| 110.1 | Serological results are not available at Day 1 for none of the serogroups | D1 | EXC | EXC (for seroresponse only) | EXC | EXC (for seroresponse only) |
| 110.2 | Serological results are not available at Day 29 for none of the serogroups | D29 | None | EXC | None | EXC |
| 112.1 | Obvious deviation from Laboratory Manual or error in laboratory data at D1 | D1 | None | None | EXC | EXC (for seroresponse only) |
| 112.2 | Obvious deviation from Laboratory Manual or error in laboratory data at D29 | D29 | None | None | None | EXC |
| 120 | Randomization failure | D1- D29 | None | None | None | EXC (for analysis at D4 and D6 only) |

Statistical Analysis Plan

Study alias & e-track number(s): V59 77 (205352)

Version: 1 Date: 19-09-2016

| PD code | PD Description | Study Period | FAS Day 1 | FAS Day 29 | PPS Day 1 | PPS Day 29 |
|---------|--|--------------|-----------|------------|-----------|------------|
| | | | FAS01FL | FAS29FL | PPS01FL | PPS29FL |
| 140 | Vaccination not according to protocol | D1 | None | None | None | EXC |
| 150 | Administration of forbidden vaccine | D1- D29 | None | None | None | EXC |
| 200 | Subject did not meet entry criteria | D1- D29 | None | None | EXC | EXC |
| 230 | Administration of forbidden medication | D1- D29 | None | None | None | EXC |
| 240 | Underlying medical condition forbidden by the protocol | D1- D29 | None | None | EXC | EXC |
| 250 | Concomitant infection related to the vaccine which may influence immune response | D1- D29 | None | None | None | EXC |
| 260 | Did not comply with study vaccination schedule | D1 | None | None | None | EXC |
| 270.1 | Did not comply with blood draw schedule at Day 1 | D1 | None | None | EXC | None |

Statistical Analysis Plan

Study alias & e-track number(s): V59 77 (205352)

Version: 1 Date: 19-09-2016

| PD code | PD Description | Study Period | FAS Day 1 | FAS Day 29 | PPS Day 1 | PPS Day 29 |
|---------|---|--------------|-----------|------------|-----------|---|
| | | | FAS01FL | FAS29FL | PPS01FL | PPS29FL |
| 270.2 | Did not comply with blood draw schedule at Day 4 or Day 6 | D4/D6 | None | None | None | EXC (for analysis at D4 and D6 only) |
| 270.3 | Did not comply with blood draw schedule at Day 29 | D29 | None | None | None | EXC |

FAS = Full Analysis Set; PPS=Per Protocol Set; EXC = excluded from this analysis set.

| | |
|--|---|
| Statistical Analysis Plan |  GSK |
| Study alias & e-track number(s): V59 77 (205352) | |
| Version: 1 | Date: 19-09-2016 |

13. ANNEX 3: STUDY SPECIFIC MOCK TFL

Not applicable
